    - For example, a participant may have an ALT of 18 U/L. Then on the next two lab draws (obtained during a study visit or unplanned visit) the values increase to 22 U/L and then 26 U/L, this increase would be enough to initiate treatment even though the values are within normal range.
    - For example, a participant may have an ALT of 38 U/L as the baseline value. Post-infusion, the ALT values are lower than that seen during screening and range from 18-22 U/L over the first few weeks. Then on the next 2 laboratory draws (obtained during a study visit or unplanned visit), the values increase to 29 U/L and then 37 U/L. This increase would be enough to initiate treatment even though the values are both below baseline and within normal range.
  - **Note:** Any delay or deviation in the initiation of corticosteroid treatment, based on the transaminase increase points above, must be discussed with the sponsor's

medical monitor in the context of the overall clinical management plan to ensure participant safety.

- FIX:C decrease, per local lab results:
  - Single significant decrease, not associated with a recent infusion of external FIX product.
    - For example, a participant may have a FIX:C of 51 IU/mL at Week 4, but at Week 5 the value decreases to 28 IU/mL. This decrease would be enough to initiate treatment.
  - Consecutive decreases (a decline in FIX activity on two consecutive blood tests independent of transaminase values) if occurring during the first 120 days post-infusion.
    - For example, a participant may have a FIX:C value of 34 IU/mL at Week 4. Then on the next two lab draws (obtained during a study visit or unplanned visit) the values decrease to 27 IU/mL and then 24 IU/mL, this decrease would be enough to initiate treatment.

If occurring beyond 120 days post-infusion, the investigator should contact the sponsor’s medical monitor to discuss prior to initiating corticosteroids unless otherwise clinically indicated (eg, a decline in FIX:C level thought to be beyond the margin of error for FIX:C assay or biological fluctuation).

- **Note:** Any delay or deviation in the initiation of corticosteroid treatment, based on the FIX:C decrease points above, must be discussed with the sponsor’s medical monitor in the context of the overall clinical management plan to ensure participant safety.

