The number of bleeding episodes (treated and untreated, excluding procedural bleeds) from Week 12 to Month 15 will contribute to the post-infusion ABR_{total} calculation for each participant, which is the primary endpoint of this study. A noninferiority test of treatment difference in ABR_{total} between pre- and post-infusion with PF-06838435 will be performed, with a NI margin of 3. The endpoint of ABR_{total} will also be calculated for the following designated time periods, such as >Month 15 to Month 24; >Month 24 to Month 36; >Month 36 to Month 48; >Month 48 to Month 60, and >Month 60 to Month 72, and considered as secondary. These secondary endpoints will be referred to as ABR_{total} Year 2, ABR_{total} Year 3, ABR_{total} Year 5, and ABR_{total} Year 6 hereafter in this document.

In addition, ABR_{total} will also be calculated and summarized for the following periods: prior to corticosteroid initiation, during corticosteroid treatment and post-corticosteroid treatment (Section 5.2) for participants in whom corticosteroid are initiated. ABR_{total} during the overall time period (Week 12 to Month 15) for participants who do not have corticosteroid treatment will be presented side by side in the same table.

For participants with incomplete data for the analysis time period, or if a participant has not yet been followed for the full length of the analysis time period, all available data during the analysis period will be annualized and summarized as such. ABR_{total} for each participant will be calculated as below:

 $ABR_{total} = (Number of bleeding episodes (treated and untreated, excluding procedural bleeds) on study during the given$ time period) x 365.25(Date of last day – date of first day +1) in that time period

Bleeding episodes associated with a surgical procedure (perioperative and/or during the surgical rehabilitation period) will not be included in the ABR_{total} calculation.

If prophylaxis FIX regimen is resumed for a participant as defined in Protocol Section 6.5.1, then the time period following the resumption of the prophylaxis regimen will be excluded from the ABR endpoint calculation, which means the bleeding events will be excluded and the time period of observation will be deducted as well. Date and reason of investigator decision to resume FIX prophylaxis will be collected in a CRF. Date of investigator decision will be considered as date of FIX prophylaxis resumption.

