Periods	Derivation of time period (Corticosteroid is initiated before Week 12 [Day 82])	Derivation of time period (Corticosteroid is initiated after Week 12 [Day 82])
prior to corticosteroid initiation	Not calculatable	date of corticosteroid initiation – Day 82
during corticosteroid treatment	date of stop of corticosteroid – Day 82 +1 *if corticosteroid is stopped before Day 82, then this time period will not be calculated.	date of stop of corticosteroid – date of initiation of corticosteroid +1
post-corticosteroid treatment	Month 15 or last contact date if has not reached Month 15 – date of stop of corticosteroid (or Day 82, whichever is later)	Month 15 or last contact date if has not reached Month 15 – date of stop of corticosteroid
overall time period	Month 15 (or last contact date if has not reached Month 15) – Day 82 +1	Month 15 (or last contact date if has not reached Month 15) – Day 82 +1

*days without corticosteroid treatment will be excluded from the derivation of corticosteroid treatment period.

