5.2.2. Analysis for Count Endpoints

For count variables such as ABR, AIR and bleeding episodes of specific types, the detailed analysis method will be discussed in Section 6. The median, the mean, interquartile range, minimum and maximum of the observed data will be reported in summary tables.

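### In the descriptive corticosteroid-period table, medians, quartiles and maxima of individually annualised ABR_total largely reflect window length; total bleeds over person-years should be the main summary (minor)

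*SAP*

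**What the plan says.** SAP 3.1.1 defines ABR_total for each participant as bleeds × 365.25 divided by the number of days in the period. For participants started on corticosteroids it "will also be calculated and summarized for the following periods: prior to corticosteroid initiation, during corticosteroid treatment and post-corticosteroid treatment (Section 5.2"), and it places the Week 12 to Month 15 value of participants without corticosteroids in the same table. When follow-up is incomplete, "all available data during the analysis period will be annualized and summarized as such".

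SAP 5.2 sets the windows. For a course begun after Day 82, *prior* is "date of corticosteroid initiation – Day 82". For a course begun earlier, *prior* is not calculated and *during* is "date of stop of corticosteroid – Day 82 +1", dropped only if the course stopped before Day 82. *Post* runs from the stop date (or Day 82, if later) to Month 15 or last contact. No minimum length is set.

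For count variables including ABR, SAP 5.2.2 states: "The median, the mean, interquartile range, minimum and maximum of the observed data will be reported in summary tables". SAP 6.1.1.2 adds only that a table will summarise ABR_total by corticosteroid period. It plans no pooled rate or person-time display for that table.

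**The concern.** An individually annualised rate from a few days is nearly always 0 and occasionally very large. The same bleeding process observed for over a year gives values spread around the true rate. Medians, quartiles and maxima from the two settings are not on a common footing, yet the table sets them side by side.

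Short windows are plausible. Protocol 8.3.8 recommends corticosteroids for consecutive FIX:C decreases "if occurring during the first 120 days post-infusion". A start on Day 83 to Day 120 gives a *prior* window of 1 to 38 days (120 − 82 = 38). Protocol Table 1 schedules eight weeks, so a 56-day course begun on Day 29 stops on Day 84 and leaves a *during* window of 84 − 82 + 1 = 3 days.

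These are the participants treated for a suspected immune response to the vector. A *prior* median of 0 beside a comparator median near 1 invites the reading that they did not bleed before corticosteroids, even if bleeding was the same in both groups.

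**Working it through.** **Inputs.** Window bounds Day 82 and Day 469 (SAP 2 and 5.2); post-infusion rate 1.5/year and background rate 5.0/year (Protocol 9.2). The documents do not give the dispersion of bleed counts, the number of corticosteroid participants, or the timing of their courses. These are assumptions below.

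**1. The SAP's bounds reproduce.** 12 × 7 − 2 = 82; (65 + 2) × 7 = 469; 469 − 82 + 1 = 388 days, or 388/365.25 = 1.062 years.

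**2. Shortest windows.** *Prior*, start on Day 83: 83 − 82 = 1 day. *During*, stop on Day 82: 82 − 82 + 1 = 1 day.

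**3. Effect of length alone, at 1.5/year.** One bleed in d days is recorded as 365.25/d. Under Poisson, P(no bleed) = exp(−1.5 × d/365.25).

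| Days | One bleed shown as (per year) | P(no bleed) |
|---|---|---|
| 1 | 365.25 | 0.996 |
| 28 | 13.0 | 0.891 |
| 38 | 9.6 | 0.856 |
| 56 | 6.5 | 0.794 |
| 388 | 0.94 | 0.203 |

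The median is 0 when P(no bleed) exceeds 0.5, that is when d < 365.25 × ln 2/1.5 ≈ 169 days. At 5.0/year the limit is 365.25 × ln 2/5 ≈ 51 days.

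**4. Equal bleeding in every column.** Simulation of 400,000 participants at 1.5/year, Poisson; assumed starts Day 20 to 150 and courses of 56 to 120 days.

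| Column | Median window (days) | Mean ABR | Median ABR | SD | Maximum | Pooled rate |
|---|---|---|---|---|---|---|
| Prior | 35 | 1.49 | 0 | 6.3 | 365 | 1.49 |
| During | 74 | 1.50 | 0 | 3.3 | 365 | 1.50 |
| Post | 297 | 1.50 | 1.27 | 1.4 | 10.9 | 1.50 |
| No corticosteroid | 388 | 1.50 | 0.94 | 1.2 | 9.4 | 1.50 |

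With negative binomial dispersion 1, the medians are 0, 0, 1.08 and 0.94, and the means stay at 1.50 to 1.51.

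**5. At trial size.** 20,000 simulated trials at 1.5/year, with ten assumed *prior* windows uniform on 1 to 38 days and 30 participants without corticosteroids:

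- The *prior* median is 0 in over 99.9% of trials, and its third quartile is 0 in about 97%.
- The comparator median averages 1.31 (Poisson) or 0.93 (dispersion 1). At dispersion 2 it averages 0.54 and is 0 in 38% of trials; at dispersion 3 it is 0 in 68%.
- When any *prior* bleed occurs, the median of the maximum is about 16/year.
- The SD of the *prior* mean of individual rates is 2.5, against 1.7 to 1.8 for the pooled rate. The variance ratio is about (2.5/1.75)² ≈ 2.
- The *prior* column contains no bleeds in 45 to 48% of trials. The Poisson check is 10 × 19.5 = 195 days = 0.534 years; 1.5 × 0.534 = 0.80 expected bleeds; exp(−0.80) = 0.45.

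**The case against.** The stakes are low. This is one descriptive supplementary table, with no test and no place in the gatekeeping sequence. The SAP's change log says only that analysis by corticosteroid period was added and states no purpose for it. SAP 5.2.2 is a general convention and no table shell is shown, so the exact statistics for this table are partly inferred. All of this stands and limits the severity.

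A reader might infer that every between-column difference is an artefact of window length. That is not so for the mean, which SAP 5.2.2 also reports: under equal bleeding it is about 1.5 in all columns. Nor is the *post* column usually affected, because its windows are mostly long.

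A reader might also expect values near 365/year. That needs a one-day window and a bleed on that day, about 0.4% at 1.5/year. A course near eight weeks gives about 6.5/year per bleed.

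The scenario of ten short *prior* windows is also open to challenge. Protocol 2.2.2 reports two of ten Phase 1/2 participants given prednisone, about 8 of 40 at that share, and starts before Day 82 have no *prior* period. The 120-day limit applies only to the consecutive FIX:C-decrease criterion, so later starts and longer windows are possible. The median contrast also weakens at higher dispersion or a lower rate. These points make the size uncertain but leave the mechanism intact.

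Finally, pooling does not cure sparse data. In this scenario its SD still exceeds the true rate of 1.5.

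**Conclusion.** The point holds as a minor presentation issue. As specified, the median, quartiles and maximum of the *prior* and *during* columns mainly reflect window length whenever those windows are short, and they should not be read against the 388-day column. The 169-day threshold rests on 1.5/year and Poisson counts. The contrast with a comparator median of about 0.9 to 1.3 rests on dispersion of about 1 or less. The doubling of variance rests on the assumed ten windows of 1 to 38 days.

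The documents do not support reading this as a threat to the main conclusions. The primary model in SAP 6.1.1.1 includes duration, and neither its result nor type I error depends on this table.

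**What to change.** In SAP 6.1.1.2, specify for this table, in each column: number of participants, total bleeds, total person-years, and the pooled rate (bleeds divided by person-years) as the main summary, with a 95% confidence interval that is valid when there are no bleeds. An exact Poisson interval would serve, with a note that it ignores overdispersion. With no bleeds in the assumed 0.534 years, its upper limit is −ln(0.025)/0.534 = 3.69/0.534 ≈ 6.9/year, which shows openly how little a sparse column can say.

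The log-link negative binomial model of SAP Appendix 1.2 should not be relied on here, because it has no finite estimate for a column with no bleeds.

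Individual medians and ranges may stay as secondary display or move to a listing, with window lengths shown. The cost is a few lines of SAP text and one table shell. No new data are needed, and the period boundaries and the primary analysis are unchanged.

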3.2. Secondary Endpoint(s)

3.2.1. ABR for Treated Bleeds

 ABR_{treat} from Week 12 to Month 15 is defined similarly as ABR_{total} except that only treated bleeding will be counted, and it is a key secondary endpoint. The estimand follows the same approach as described for ABR_{total} . A noninferiority test of treatment difference in ABR_{treat} between pre- and post treatment with PF-06838435 will be performed similarly as ABR_{total} , with a NI margin of 3.

ABR for treated bleeds will also be calculated and analyzed similarly as ABR_{total} for >Month 15 to Month 24; >Month 24 to Month 36; >Month 36 to Month 48; >Month 48 to Month 60, and >Month 60 to Month 72.

3.2.2. Annualized Infusion Rate (AIR)

Annualized infusion rate of exogenous FIX from Week 12 to Month 15 is considered as a key secondary endpoint. All infusions during the observation time period for any purpose including: to treat bleeding, or for preventive purpose, or perioperative, or if prophylaxis FIX regimen is resumed, will be included in the calculation of AIR. Similar endpoints will be calculated for the subsequent time periods, >Month 15 to Month 24; >Month 24 to Month 36; >Month 36 to Month 48; >Month 48 to Month 60; and >Month 60 to Month 72. AIR calculated for the above time period will be referred to as AIR Year 2, AIR Year 3, AIR Year 4, AIR Year 5, and AIR Year 6.

For participants with incomplete data for the analysis time period, or if a participant has not yet been followed for the entire analysis time period, all infusion data during that period will

be included in the analysis and summarized as such. AIR for each participant will be annualized as below:

AIR= (Number of infusions (for any reason) during the given time period x 365.25) (Date of last day – date of first day +1) in that time period)

Similarly, the baseline AIR data will be based on data collected in the Pre-Infusion Period while participants were on a prophylaxis FIX replacement regimen. For the baseline AIR calculation, all infusions will be included in the AIR calculation including those to treat bleeding (on-demand), for prophylaxis, for preventive purposes, or perioperative infusions. The AIR baseline will be annualized using the above formula.

The list of participants who resumed FIX prophylaxis and the date of resumption will be confirmed and provided to the programming team by the clinical team before database release. The percentage of the participants who resume a FIX prophylaxis regimen will be determined for the overall time period.

3.2.3. FIX:C

All samples collected from participants for plasma FIX:C as defined in Protocol Section 1.3 SoA will be analyzed both at local and central lab. FIX:C results obtained from local labs will be used for patients care purpose, while the central lab results will be included in the analysis. The certified central clinical laboratory will analyze the sample by two one-stage assays and a chromogenic assay. The first one-stage assay was performed on BCSXP analyzer with Actin-FSL reagent. The second one-stage assay will use the same analyzer but will use 'SynthAsil' as reagent. Data from all three assays will be summarized and presented, while the FIX:C data using one-stage assay (Actin-FSL reagent on BCSXP analyzer), which was also used in the phase 1/2 study C0371005 and long-term follow-up study C0371003, will be the primary result used for hypothesis testing. Any sample taken within 7 days after (14 days if extended half-life [EHL] product is used) exogenous FIX replacement therapy administered for any purpose (including treatment of bleeding, preventive purpose, or resumption of FIX prophylaxis regimen) will be excluded from the analysis of FIX: C.

The steady state FIX:C is calculated for each participant as the geometric mean of all eligible FIX:C measures from 12 weeks [Day 82] to Month 15 [Day 469] inclusive after PF-06838435 infusion. If a participant withdrew consent, dropped out early from the study or resumed FIX prophylaxis, then the assessments at the visits following withdrawal/dropout/resumption will be imputed as 1.9%. The calculation contains all FIX measurements (scheduled and unscheduled) within the visit window of Week 12 through the visit window of Week 65 (Week 12 \pm 2 days [Day 82] and Week 65 \pm 2 weeks [Day 469]). This key secondary endpoint will be referred to as steady state FIX:C hereafter in this document. For the primary analysis, assessments with missing data imputation will be utilized. Another analysis will also be conducted with only observed data as supportive analysis.

FIX:C will also be analyzed based on all eligible measurements in the designated time periods such as >Month 15 to Month 24; >Month 24 to Month 36; >Month 36 to Month 48; >Month 48 to Month 60, and >Month 60 to Month 72 as secondary endpoints. The geometric mean of all eligible FIX:C measures during the above time periods will be calculated for each individual participant and then summarized across participants. These secondary endpoints will be referred to as FIX:C Year 2, FIX:C Year 3, FIX:C Year 4, FIX:C Year 5, and FIX:C Year 6 hereafter in this document. If a participant has not yet been followed to the full year or has missing data, then all available data for that time interval will be included to calculate geometric mean despite the missed measurements.

The geometric mean of all eligible FIX:C measures will also be calculated and summarized for the following periods: prior to corticosteroid initiation, during corticosteroid treatment and post-corticosteroid treatment (Section 5.2) for participants in whom corticosteroid are initiated. Steady state FIX:C during the overall time period for participants who do not have corticosteroid treatment will be presented side by side in the same table.

In addition, absolute value of FIX:C will be summarized over time by study visit. If multiple assessments exist for a study visit, the average value will be calculated. If a participant withdrew consent, dropped out early from the study or resumed FIX prophylaxis, then the missing assessment will be imputed as 1.9%. For the primary analysis, assessments with missing data imputation will be utilized for summaries. Another analysis will also be conducted with only observed data as supportive analysis.

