	
 
• Change in joint health as measured by the Hemophilia Joint Health Score (HJHS) instrument.
 
• PRO instruments:               
 
• Haem-A-QoL Physical Health domain;
 
• HAL Complex Lower Extremity Activities Component Score.
 
 
 

 
• Safety and tolerability of PF-06838435, including immunogenicity, for the study duration of 6 years after PF-06838435 infusion
 
	
 
• Incidence and severity of adverse events collected during the study, as per details provided in Section 10.3.3.
 
• Adverse Events of special interest:               
 
• Hypersensitivity reactions;
 
• Clinical thrombotic events;
 
• FIX inhibitors,
 
• Hepatic malignancies.
 
• Drug related elevated hepatic transaminases that fail to improve or resolve
 
• Malignancy assessed as having reasonable possibility of being related to study drug
 
 
 
• Other immunogenicity-based laboratory data including: neutralizing antibody (nAb) to AAV capsid, immune response (presumed T-cell activation) to AAV capsid protein and/or FIX transgene
 

 
• Assess durability of efficacy up to 6 years.
 
	
The following parameters will be assessed throughout the 6-year study period according to the SoA. Summaries will be provided for the overall follow-up period, as well as by yearly intervals:
 
 
• Annualized Bleeding Rate for total bleeds (treated and untreated).
 
• ABR for treated bleeds.
 
• AIR of exogenous FIX.
 
• Vector-derived FIX:C level by study visit and the geometric mean at each yearly interval.
 
• Annualized FIX consumption.
 
• Annualized number of bleeding events of specific type: spontaneous and traumatic, and untreated.
 
• HJHS total score.
 
• Frequency of target joint bleeds.
 
• PROs instruments.
 
• Haem-A-QoL Physical Health domain.
 
• HAL Complex Lower Extremity Activities Component Score.
 

Objectives	Endpoints
Tertiary/Exploratory	Tertiary/Exploratory

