5.3. Methods to Manage Missing Data

In general, missing data will not be imputed in this study, unless specified in Section 3, where individual endpoints are discussed.

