6.2.3.2. Sensitivity/Supplementary Analyses

Similar analyses comparing the FIX:C Year 2 to 6 to the threshold of 5% will be conducted. The window for Year 2 will be from Month 15 through Month 24 as previously described. The above analysis will be conducted on Dosed population.

Similar summaries will also be provided for FIX:C during the following periods: prior to corticosteroid initiation, during corticosteroid treatment and post-corticosteroid treatment (Section 5.2) for the participants in whom corticosteroid is initiated. FIX:C during the overall time period (Week 12 to Month 15) for participants who do not have corticosteroid treatment will be presented side by side in the same table.

An individual plot will be generated to visualize FIX:C values of the Dosed population. The graph will display all FIX:C measurements excluding the ones within the window of FIX infusion.

Actual value of FIX:C will be presented in a summary table by study visit with mean, SD, 95% CI of the mean, median, min, max, Q1 and Q3. A box-whisker plot will also be provided for data visualization purpose. In addition, a stacked bar graph will be generated by study visit, presenting percentage of participants falling into the following category (FIX:C: 0-<5%, 5-<15%, 15-<50%, 50-<150%, $\geq 150\%$). If a participant withdrew consent, dropped out early from the study or resumed FIX prophylaxis, then the missing assessment will be imputed as 1.9%. For the primary analysis, assessments with missing data imputation will be utilized for summaries. Another supportive analysis will also be conducted with only observed data.

The FIX:C results by two different one-stage assays along with analysis by chromogenic assay will be visualized in graphs with chromogenic value on the x-axis and both one-stage assay results on the y-axis. The FIX:C results of two-stage assays will be visualized using scatter plot.

The Pearson's correlation will be calculated for each pair of the three assays.

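### The Year 2–6 FIX:C geometric means omit the 1.9% rule used for the other FIX:C summaries, so participants who resumed prophylaxis largely drop out and the yearly level is biased upward

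*SAP*

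**What the plan says.** Protocol Section 3 has the secondary objective "Assess durability of efficacy up to 6 years". Its FIX:C endpoint has two parts: the level by study visit and the geometric mean in each yearly interval.

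SAP 3.2.3 handles missing FIX:C in three ways.

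- **Steady state, Week 12 to Month 15.** If a participant withdraws, drops out or resumes prophylaxis, "then the assessments at the visits following withdrawal/dropout/resumption will be imputed as 1.9" per cent. An observed-data analysis is supportive.
- **Yearly geometric means, Years 2 to 6.** The rule reads: "If a participant has not yet been followed to the full year or has missing data, then all available data for that time interval" go into the geometric mean, whatever measurements were missed. The paragraph has no 1.9% rule and no paired analysis.
- **By-visit values.** After the same three events, "then the missing assessment will be imputed as 1.9" per cent. Observed data are again supportive.

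SAP 5.3 gives the default: "In general, missing data will not be imputed in this study, unless specified in Section 3". SAP 6.2.3.2 adds: "Similar analyses comparing the FIX:C Year 2 to 6 to the threshold of 5% will be conducted".

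Two further rules matter. SAP 3.2.3 excludes from the FIX:C analysis "Any sample taken within 7 days after (14 days if extended half-life [EHL] product is used) exogenous FIX replacement therapy administered for any purpose", and it lists resumed prophylaxis among those purposes. Protocol 6.5.1 allows resumption when the gene therapy is judged not efficacious, on either a FIX activity criterion or a bleed-count criterion.

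**The concern.** Loss of expression is what the durability objective has to detect. It is also a main reason for resuming prophylaxis, and a participant on regular FIX dosing will have few or no samples outside the 7- or 14-day exclusion. In the year he resumes he still contributes his earlier samples. In later years he contributes little or nothing. The yearly geometric mean then describes mainly those who are still expressing.

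Two consequences follow. The yearly level is too high, and the trend can be wrong: the summary can rise after Month 15 only because low values have left it. The by-visit summary and the yearly summary would also describe the same participants under different rules.

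A practical point adds to this. Under Protocol 8.1.1, prophylactic infusions need not be reported after Week 78, so the dates needed to apply the wash-out exclusion may be missing in the later years. The yearly paragraph gives no separate rule for samples taken after resumption.

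**Working it through.** **Inputs.**
- N = 40 (Protocol 9.2).
- Imputed value 1.9% (SAP 3.2.3).
- Level in participants still observed: 33.7 ± 18.5%, range 14 to 81 (Phase 1/2, Protocol 2.2.2). Carrying this into Years 2–6 is an assumption.
- k = number of participants with no eligible sample in a given year. The documents give no expected value, so a range is shown.

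**The plan's own figure.** SAP 6.2.2.2 equates more than 20% resuming with about 8 participants: 0.20 × 40 = 8, which reproduces. The documents give no sample size or power for yearly FIX:C.

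**Log-scale parameters, assuming a lognormal distribution.** (18.5/33.7)² = 0.301. The log-SD is √ln(1.301) = 0.513, and the geometric mean is G = 33.7/√1.301 = 29.54%.

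**Yearly geometric mean.** On available data it is G, whatever k is. Under the 1.9% rule it is exp{[(40 − k) ln G + k ln 1.9]/40}. The ratio of the two is (G/1.9)^(k/40).

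| k | Available data | 1.9% rule | Ratio |
|---|---|---|---|
| 1 | 29.54% | 27.58% | 1.07 |
| 2 | 29.54% | 25.75% | 1.15 |
| 4 | 29.54% | 22.45% | 1.32 |
| 6 | 29.54% | 19.57% | 1.51 |
| 8 | 29.54% | 17.06% | 1.73 |

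With G at the ends of the Phase 1/2 range (14% and 81%), the ratio is 1.05 to 1.10 at k = 1 and 1.49 to 2.12 at k = 8.

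**Arithmetic mean of participant values.** This is [(40 − k) × 33.7 + k × 1.9]/40. It gives 32.91% at k = 1 and 27.34% at k = 8, against 33.7% on available data. The overstatement is 2.4% and 23.3%.

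**Trend.** Suppose 8 participants averaged 5% up to Month 15 and then left the mean. The steady-state summary is exp(0.8 ln 29.54 + 0.2 ln 5) = 20.7%. The later yearly value is 29.5%, with no change in anyone else.

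**Resumption within a year.** Suppose a participant has 5% at Week 78 and then resumes. His Year 2 value is 5.0% on available data. With Weeks 91 and 104 set to 1.9% it is (5 × 1.9 × 1.9)^(1/3) = 2.62%.

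**Test against 5% at k = 8, log scale.**
- Available data: t = (ln 29.54 − ln 5)/(0.513/√32) = 19.6.
- 1.9% rule: mean log = ln 17.06 = 2.837. Sample variance = [32 × 0.513² + 32 × (3.386 − 2.837)² + 8 × (0.642 − 2.837)²]/39 = 1.45, so SE = 0.1905. Then t = (2.837 − 1.609)/0.1905 = 6.44, and the lower 95% limit is 11.6%.

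The conclusion is the same under both rules.

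**The case against.** The best counter-argument is that the SAP is ambiguous rather than wrong. The yearly sentence speaks of short follow-up and missed measurements and does not name resumption. SAP 6.2.3.2 calls the yearly analyses similar to the main one, in which imputation is primary. This does not settle the matter. SAP 5.3 requires imputation to be specified in Section 3, and the Section 3 paragraph on yearly means specifies available data. The general word in 6.2.3.2 does not override it, and reading it that way would create a conflict that still needs correction.

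Other points stand and limit the finding.

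- Failures are visible elsewhere. The by-visit FIX:C summary imputes 1.9% and has a 0 to <5% category. AIR counts resumed prophylaxis infusions, and the percentage resuming is reported by interval.
- The Year 2–6 comparisons with 5% are listed under sensitivity and supplementary analyses and lie outside the gatekeeping sequence of SAP Table 2.
- The 20% figure is a trigger for an extra summary, not an expected rate. With one failure the effect is small.
- Protocol 6.5.1 allows resumption on bleeds alone and allows prophylaxis to be stopped again. A blanket 1.9% rule would overwrite valid later samples.
- Withdrawal unrelated to expression need not bias upward, and 1.9% carried for up to five years is a strong assumption for it.

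**Conclusion.** The concern holds for the yearly geometric means. For participants who resumed for lack of expression the direction is upward. The size depends on how many there are: about 1.07-fold with one, 1.3-fold with four and 1.7-fold with eight of 40, assuming Phase 1/2 levels persist in the others and that those who resumed have no eligible sample that year.

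A reader might infer that the Year 2–6 tests would wrongly show FIX:C above 5%. The calculation does not support that: with eight failures imputed, the lower limit is still 11.6%. A reader might also infer that the plan hides loss of durability altogether. It does not, because the by-visit FIX:C, AIR and resumption summaries show it. What is biased is the size and time trend of one named durability summary.

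**What to change.** Amend the yearly paragraph of SAP 3.2.3 and align SAP 6.2.3.2.

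- **Resumed prophylaxis.** Impute 1.9% at the protocol-scheduled FIX:C sampling times in Years 2–6 while the participant remains on prophylaxis. Keep any eligible washed-out samples obtained after prophylaxis is stopped again. The resumption date is already collected on a CRF, and the prescribed regimen continues to be captured after Week 78, so the rule need not rely on individual infusion dates.
- **Withdrawal or dropout.** Apply the same 1.9% rule for consistency with Week 12 to Month 15, or show it as a sensitivity analysis.
- **Not yet followed through the interval.** Keep available data.
- **Reporting.** Make this the main yearly summary, with observed-only as supportive, and give the number of observed and imputed participants for each year.

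The cost is a short SAP amendment. The 1.9% convention is already needed for the other two FIX:C summaries, but the yearly version needs the sampling times and the on/off prophylaxis periods defined. The downside is that yearly figures become less favourable and depend on the 1.9% convention.
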